# 9.3.6.5.2 Pregnancy

For safety reporting purposes, any pregnancy occurring during the study will be considered an "important medical event" (Section 9.3.6.5.1). If a study subject becomes pregnant while participating in the study, the study drug will be discontinued immediately and the pregnancy will be reported to the Sponsor. The Investigator will then report follow-up information to the Sponsor regarding the course of the pregnancy, including perinatal and neonatal outcome, regardless of the fact that the subject has discontinued the study. Once the newborn is determined to be healthy, as defined by and agreed upon by the Sponsor and Investigator, additional follow-up will no longer be required.

# 9.3.6.5.3 Serious Unexpected and Suspected Adverse Reaction

An unexpected AE (or serious and unexpected suspected adverse reaction [SUSAR]) is any AE or suspected adverse reaction that is not listed in the IB or is not listed at the specificity or severity that has been observed, if an IB is not required/available, is not consistent with the risk information described in the general investigational plan. This also refers to AEs or suspected adverse reactions mentioned in the IB as occurring with a class of drugs or as anticipated from the pharmacological properties of the drug but are not specifically mentioned as occurring with the study drug. A SUSAR requires mandatory expedited reporting to the applicable regulatory authority(ies) (Section 9.3.6.8). The Sponsor will forward the formal notification describing the SUSAR to Investigators. Each Investigator must then notify his/her IRB of the SUSAR, in accordance with the IRB's policy.

The Sponsor should be notified within 24 hours of the Investigator becoming aware of a SUSAR and the event documented on the CRF.

# 9.3.6.6 Recording Adverse Events

All AEs (including SAEs) within the 5 pre-surgery visits are to be accurately recorded on the AE/SAE page(s) of the CRF. In addition, any SAEs within 30 days of visit 5 will need to be recorded. The Investigator will carefully evaluate each AE to determine:

- Duration (start and end dates)
- Severity (grade)
- Seriousness
- Relationship to study drug (Not Related, Possible, Definite)
- Action taken (none, study drug modification, medical intervention)
- Outcome (resolved without sequelae, resolved with sequelae, ongoing)

The Investigator will evaluate the recorded AEs and SAEs with regard to maximum intensity and relationship to study drug. Maximum intensity should be assigned using one of the severity grades as outlined in the NCI CTCAE v4.0. If the AE is not specifically listed in CTCAE v4.0, the following grades will be used:

- Grade 1: mild
- Grade 2: moderate

- Grade 3: severe
- Grade 4: life-threatening or disabling
- Grade 5: death

## 9.3.6.7 Determining Relationship of Adverse Events to Study Drug

The Investigator must attempt to determine if an AE or SAE is related to the use of the study drug. This relationship should be described as follows:

- **Possible** The event follows a reasonable temporal sequence from administration of the study drug and the event follows a known response pattern to the study drug BUT the event could have been produced by an intercurrent medical condition which, based on the pathophysiology of the condition and the pharmacology of the study drug, would be unlikely to be related to the use of the study drug OR the event could be the effect of a concomitant therapy.
- **Definite** The event follows a reasonable temporal sequence from administration of the study drug, the event follows a known response pattern to the study drug and based on the known pharmacology of the study drug, the event is clearly related to the effect of the study drug.

*Not Related* Based on the evidence available, causality is not possible.

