#### 6.2 Discussion of Trial Design

This study is intended to establish the first-in-human safety and efficacy observations and the optimal dose of the PRV111 (Cisplatin Transmucosal System) prior to the surgical removal of SCC tumors of the oral cavity.

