#### Table 2. Dosing Terminology

#### 8.2 Dose-limiting Toxicity (Stopping Rules for an Individual Subject)

Toxicity will be graded and recorded according to the NCI CTCAE version 4.03 (US Department of Health and Human Services, 2010), which are considered at least possibly related to PRV111 Patch. A DLT is defined as a clinically significant Treatment-Emergent AE (TEAE) or laboratory abnormality unrelated to disease progression, concurrent illness, or concomitant therapy and that meets any of the following criteria:

• Grade 3 or 4 non-hematologic toxicity excluding alopecia

- Grade 3 or 4 nausea, vomiting, or diarrhea, lasting >48 hours, despite standard prophylaxis and/or treatment (refer to Section 8.7 for a list of suggested anti-emetic medications)
- Grade 4 neutropenia lasting >5 days.
- Febrile neutropenia, defined as absolute neutrophil count <1000/mm^3 with a single temperature of >38.3°C (101°F) or a sustained temperature of ≥38°C (100.4°F) for more than 1 hour.
- Grade 4 thrombocytopenia or thrombocytopenia with clinically significant bleeding (ie, bleeding that requires blood or platelet transfusion or other medical intervention, or that may cause disability or death, such as cerebral hemorrhage).
- Any toxicity that precludes administration of at least 3 of the 4 planned applications.
- Grade 4 local toxicity- oral mucositis according to World Health Organization scale:
  - Grade 0 No oral mucositis
  - o Grade 1 Erythema and soreness
  - Grade 2 Ulcer, able to eat solids
  - Grade 3 Ulcers, requires liquid diet (due to mucositis)
  - Grade 4 Ulcers, alimentation not possible (due to mucositis)
- Any related AE leading to surgery delay for more than 96 hours is a DLT

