#### 9.3.6.2 Suspected Adverse Reaction

A suspected adverse reaction is a subset of all AEs for which there is a reasonable possibility (ie, evidence to suggest a causal relationship between the drug and the AE) that the drug caused the event. Suspected adverse reaction implies a lesser degree of certainty about causality than adverse reaction.

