4.6.10 Determining Relationship of Adverse Events to Study Drug

The Investigator must attempt to determine if an AE or SAE is related to the use of the study drug. This relationship should be described as follows:

- Possible** The event follows a reasonable temporal sequence from administration of the study drug and the event follows a known response pattern to the study drug BUT the event could have been produced by an intercurrent medical condition which, based on the pathophysiology of the condition and the pharmacology of the study drug, would be unlikely to be related to the use of the study drug OR the event could be the effect of a concomitant therapy.
- Definite** The event follows a reasonable temporal sequence from administration of the study drug, the event follows a known response pattern to the study drug and

based on the known pharmacology of the study drug, the event is clearly related to the effect of the study drug.

Not Related Based on the evidence available, causality is not possible.

4.7 Adverse Events Analysis:

All treatment-emergent adverse events (TEAE) will be summarized. Counts and percents of each observed system organ class (SOC) and preferred term as defined in the Medical Dictionary for Regulatory Activities (MedDRA) version 9.0 or later will be presented. The preferred terms will be summarized in the following sets of tables:

- Baseline AEs, occurring after enrolment and prior to treatment;
- All TEAEs;
- All serious TEAEs;
- All TEAE leading to discontinuation from study
- All TEAEs by closest relationship (related or not related). Relationship will be recorded as definitely related, probably related, possibly related, or not related to the study medication; the recorded relationship will be included in listings.

Reported severity (mild, moderate or severe) will be included in the listing. The severity of the TEAEs will be graded according to the CTCAE criteria, version 4.0 (Appendix 3). A separate table for AE of CTCAE grade greater than 2 (moderate) will be generated. The severity of oral mucositis will be graded according to the WHO grade.

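### The relatedness scale has no level for a plausible but previously unseen toxicity, and on a literal reading such events can drop out of the DLT count

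*Protocol*

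**What the plan says.** Protocol 9.3.6.7 and SAP 4.6.10 define the levels in the same way:

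- **Possible:** plausible timing and "the event follows a known response pattern to the study drug BUT the event could have been produced by an intercurrent medical condition" or could be an effect of concomitant therapy.
- **Definite:** plausible timing, "the event follows a known response pattern to the study drug and based on the known pharmacology of the study drug" the link is clear.
- **Not Related:** "Based on the evidence available, causality is not possible".

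The CRF item in Protocol 9.3.6.6 (SAP 4.6.9) offers these three levels only. SAP 4.7 instead expects four: "Relationship will be recorded as definitely related, probably related, possibly related, or not related to the study medication". The extra level is not defined anywhere. SAP 4.7 then tabulates events as related or not related, and SAP section 7 states that no departures from the protocol are planned.

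Protocol 8.2 (SAP 2.10) introduces DLTs by way of graded toxicities "which are considered at least possibly related to PRV111 Patch". Its next sentence requires that a DLT not be attributable to disease progression, concurrent illness or other therapy, and that it meet a listed criterion. Elsewhere the Protocol uses another causal standard. In 9.3.6.2, "A suspected adverse reaction is a subset of all AEs for which there is a reasonable possibility" of drug causation, with no condition about a known pattern. Protocol 6.2 describes the setting: "This study is intended to establish the first-in-human safety and efficacy observations".

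**The concern.** Both related levels presuppose that the drug is already known to produce the event in question. In a first-in-human study, the events of most interest include those nobody has yet seen. Protocol 4.3 lists recognised toxicities of intravenous cisplatin (renal, ototoxic, myelosuppressive), so systemic events of those kinds have a pattern to follow. That experience gives little guidance for a mucosal patch used with a permeation enhancer. The gap therefore concerns mainly novel local, enhancer or patch effects.

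The rating matters beyond the safety tables. Under Protocol 6.1 the Stage 1 and Stage 2a decisions turn on whether two subjects have DLTs. Under Protocol 10.5.3 the incidence of DLTs is part of the primary endpoint. If the scale does not say how to rate an event, an individual convention may decide whether that event is counted.

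**Working it through.** The plan gives no figure to reproduce, so the main check is of the text.

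**1. Apply the definitions to each kind of event with plausible timing.**

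| Known pattern? | Alternative cause? | Link clear? | Level met |
|---|---|---|---|
| Yes | Yes | No | Possible |
| Yes | No | Yes | Definite |
| Yes | No | No | None |
| No | No | Any | None |
| No | Yes | Any | None, on the natural reading |

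In the last three rows Not Related is also unavailable unless causality can be ruled out. In the last row one could read the final clause of Possible, on concomitant therapy, as sufficient on its own. That would rescue some events in that row but none in the two rows above it.

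**2. Carry this to the DLT definition.** Section 8.2 uses the language of possible relatedness but does not cite 9.3.6.7. Possible is defined nowhere else, and it is the level an investigator has to tick. If 8.2 is read through 9.3.6.7, an event in the last three rows does not qualify.

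**3. Compare the exclusion wording in 8.2.** A DLT must be unrelated to concurrent illness or concomitant therapy. A Possible event is by definition one that such a cause could have produced. Read together, only Definite events pass without argument, and Definite needs a known pattern.

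**4. Conditional example.** Suppose two of five Stage 1 subjects have the same Grade 3 toxicity with no known pattern. Rated on reasonable possibility, there are 2 DLTs and the two-or-more branch of 6.1 applies. If a strict literal reading leaves both unrated and uncounted, there are 0 and the fewer-than-two branch applies. That branch leads to escalation with 2 or fewer responders, and to the same dose with 3 or more.

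**5. Size, for illustration.** Let p be the true DLT rate and s the share of DLTs not counted; both are assumed. With q = p(1 − s), the chance of counting at least 2 in 5 is 1 − (1 − q)^5 − 5q(1 − q)^4. For p = 0.33 and s = 0 this is 1 − 0.1350 − 0.3325 = 0.5325.

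| True rate p | s = 0 | s = 0.25 | s = 0.50 |
|---|---|---|---|
| 0.20 | 0.2627 | 0.1648 | 0.0815 |
| 0.33 | 0.5325 | 0.3619 | 0.1930 |
| 0.40 | 0.6630 | 0.4718 | 0.2627 |
| 0.50 | 0.8125 | 0.6185 | 0.3672 |

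**6. Check the reporting route.** Protocol 9.3.6.5.3 defines a SUSAR by absence from the Investigator's Brochure. Section 9.3.6.8.1 sends every SAE during treatment or within 30 days to the sponsor whatever its relationship. Under 9.3.6.11 the sponsor also assesses causality. None of these requires a known pattern. Section 9.3.6, however, makes IRB and FDA reporting depend on the event being at least possibly related to study participation, which is a further formulation.

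**The case against.** A reader might infer that a novel toxicity cannot become a SUSAR. The documents do not support that: the route in step 6 is independent of the 9.3.6.7 scale, and being unlisted is what makes an event unexpected. Unanticipated device effects also have their own definition in 9.3.6.4.

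A reader might also infer that the scale forces such events into Not Related, so that the DLT count is zero. That does not follow either. Not Related requires that causality be impossible, which a well-timed, unexplained event does not meet. The event is unclassifiable, and an investigator obliged to choose might well choose Possible.

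The link to the DLT count is itself an inference. Section 8.2 has no cross-reference, and its defining sentence works by exclusion. A novel Grade 3 non-hematologic event with no other cause satisfies that sentence directly. Oral mucositis is a named criterion in 8.2. Under 8.3 the Medical Monitor and investigators may reduce the regimen for safety at any time, and 7.6 allows termination for unexpected risk. All TEAEs are tabulated, with a separate table above Grade 2, so no event disappears from the data.

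These points stand, and they limit the claim to a literal reading and mainly to novel effects. They do not remove it. The discretionary safeguards do not define who counts as having a DLT, and 8.2 supports two readings with different counts. SAP 4.7 also has only two bins for an event that fits neither. The unused fourth level in SAP 4.7 is a minor mismatch, because that table collapses the levels anyway.

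**Conclusion.** The concern holds in a limited form. As written, the three levels have no place for a plausible but previously unseen toxicity, nor for a known-pattern event with no alternative cause and a link short of clear. On a literal reading, such events can drop out of the DLT count that drives the Stage 1 and Stage 2a decisions and out of the related-event table. The exclusion wording in 8.2 also conflicts with a Possible level defined by alternative causes. SUSAR reporting is not blocked; the fault there is that 8.2, 9.3.6, 9.3.6.2 and 9.3.6.7 use causality standards that are not aligned.

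The size cannot be fixed from the documents. The table in the working assumes the true DLT rate, the uncounted share, five subjects at risk and independent outcomes. The two-of-five example also depends on the strict literal reading. What makes the point worth acting on is that a threshold of two subjects is sensitive to how one or two events are rated.

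**What to change.** - In Protocol 9.3.6.7 and SAP 4.6.10, remove the known-pattern condition from Possible. Tie the level to the reasonable-possibility standard of 9.3.6.2, with or without another possible cause.
- State that any event that does not meet Not Related is at least Possible.
- State in Protocol 8.2 (and its copy in SAP 2.10) that relatedness there means this standard, and reconcile the exclusion wording with it. The listed toxicity criteria need no change for this purpose.
- Bring the reporting wording in Protocol 9.3.6 into line with the same standard.
- Reduce SAP 4.7 to the three levels collected, and say which of them count as related.

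The cost is wording in a few sections of each document, plus CRF guidance. Slightly more events will be rated related, so the DLT thresholds may be reached somewhat more often.

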## 9.3.6.8 Reporting Deaths and Other Serious Adverse Events

#### 9.3.6.8.1 Events to Be Reported and Timeframe

Any death or other SAE experienced by the subject during treatment or within 30 days of receiving study drug, regardless of expectedness, relationship to study drug, or any death that occurs more than 30 days after receiving study drug and is believed to be study drug-related, must be promptly reported to the Sponsor (*within 24 hours (of a working day) of the Investigator becoming aware of the event*) by telephone or email transmission.

# 9.3.6.8.2 Governing Regulatory Requirements

Compliance with this request for prompt reporting is essential in that the Sponsor is responsible for informing the FDA and other regulatory authorities as well as all other participating Investigators of the event.

Under FDA ruling (US CFR, Title 21 CFR Part 312.32) and the International Council on Harmonisation (ICH) Guidelines for Clinical Safety Data Management Definitions and Standards for Expedited Reporting, the Sponsor is required to submit written documentation, in the form of an IND Safety Report, on the following:

- SUSARs
- Unexpected fatal or life-threatening suspected adverse reactions
- Findings from other studies that suggest a significant risk to humans exposed to drug

- Findings from animal or in vitro testing that suggest a significant risk to humans exposed to drug
- Increased rate of occurrence of serious suspected adverse reactions from what is reported in the IB or the Protocol

Written submission must be made by the Sponsor to the FDA/other regulatory authorities (and by the Investigator to the IRB) as soon as possible, and in no event later than 15 calendar days after the Sponsor determines that the information qualifies for reporting. The Sponsor shall also inform all Investigators.

In addition, the Sponsor is further required to report, by either telephone or facsimile transmission or in writing to the FDA/other regulatory authorities the occurrence of any unexpected fatal or life-threatening event associated with the use of the drug (SUSARs) no later than 7 calendar days after notification of the event, followed by a written report no later than 15 calendar days after the initial report receipt date. The Sponsor shall also inform all Investigators.

The Sponsor will provide expedited reports of the following SUSARs to the Investigators for reporting to their IRB:

- SUSARs that have arisen in the clinical trial that was assessed by the IRB.
- SUSARs that have arisen in other clinical trials of the same Sponsor and with the same medicinal product, and that could have consequences for the safety of the subjects involved in the clinical trial that was assessed by the IRB.

Investigators are required to promptly report to the IRB all unanticipated problems involving risk to human subjects, including AEs that should be considered unanticipated problems (21 CFR 312.53(c)(1)(vii), 312.66, and 21 CFR 56.108(b)(1)).

# 9.3.6.9 Initial Information Provided by the Investigator

The Investigator must transmit sufficient initial information to the Sponsor (or designee) should an SAE report meet the criteria for completion of an IND Safety Report. As much of the following information about the subject and the event will be requested:

- Subject identification code, gender, and age or date of birth
- Underlying diagnosis and extent of disease
- Lot number and expiration date of study drug (if available)
- Dose, route, frequency, and duration of study drug administered
- Date of last study drug administration
- Description of event, including date of onset and duration
- Date of death (if applicable)
- Intervention(s) required
- Concomitant therapy (including regimens and indications)
- Pertinent laboratory data/diagnostic study (including dates)
- Pertinent medical history
- Study drug status (dose interrupted, discontinued)

Confidential Property of Privo Technologies, Inc. Page 45 of 59

- Did event abate after interruption of study drug administration (if applicable)?
- Did event recur after study drug was reintroduced (if applicable)?
- Severity of the AE
- Relationship of the AE to study treatment
- Outcome of the AE

## 9.3.6.10 Follow-up Information

Follow-up data concerning the SAE (eg, diagnostic test reports, physician's summaries, etc.) must also be submitted to the Sponsor as they become available by email as soon as they become available, and until the event resolves or stabilizes.

#### 9.3.6.11 Serious Adverse Event that are Unexpected and related Serious Adverse Reaction Review that have a Potential Impact on Trial Conduct

The Investigator will review each SAE report and evaluate further the relationship of the SAE to study drug and to the subject's underlying disease.

Based on the Investigator's and Sponsor's assessment of causality of the AE and discussions with the Medical Monitor, a decision will be made by the Sponsor concerning the need for further action with respect to the future conduct of the study. The primary consideration governing further action is whether new findings affect the safety of other subjects participating in the clinical study. If the discovery of a new SAE related to study drug raises concern over the safety of its continued administration to subjects, the Sponsor will take immediate steps to notify FDA, other regulatory authorities, and all Investigators participating in clinical studies with the study drug.

Further action required may include any of the following:

- Alteration of the existing research program by modification of the Protocol
- Discontinuation or suspension of the study
- Alteration of the informed consent process by modification of the existing consent form and informing current study participants of new findings
- Modification of previously identified expected suspected adverse reaction lists to include SAEs newly identified as study drug-related

#### 9.4 Pharmacokinetics Assessment

#### 9.5 Technical Success Assessments

Technical assessment data will include:

- Taste of the PE solution
- Taste of the PRV111 patch
- Adhesion, including the time of adhesion of PRV111 patch
- PRV111 patch peel-off
- Residual cisplatin level in the patch after the application period. All PRV111 patches will be assessed for the amount of residual cisplatin in each patch after each application period. If the product detaches prematurely, the residual cisplatin will be assessed and the time of detachment will be noted.

#### 9.6 Timing of Assessments

Refer to Table 1 for a schedule of events.

## 9.6.1 Screening (Visit 0)

- Visit and all historical exams/tests must occur within 28 days prior to initial treatment (Visit 1). Confirmed SCC
- Obtain and document consent from potential subject on Informed Consent Form (ICF)
- Review inclusion/exclusion criteria to determine eligibility
- Review demographics, medical and medications history to determine eligibility based on inclusion/exclusion criteria
- Obtain or perform a general physical examination (must be within 14 days of first dose) and check VS
- Perform a systematic and thorough visual and manual examination of the oral cavity mouth and cervical and local lymph nodes examination
- Obtain historical or perform an ECG
- •
- Perform clinical labs: blood draw for complete blood count (CBC), chemistry panel (creatinine for determining creatinine clearance, blood urea nitrogen (BUN), liver function test (LFT), electrolytes [potassium, magnesium, calcium, and sodium], hCG [serum]) for females of childbearing potential and perform urinalysis.
- AE documentation begins after subject signs the ICF
- Schedule study visits
- Obtain historical or test tissue for HPV

